Clinical Trial Protocol: THR-1442-C-418

Study Title: Efficacy and safety of EGT0001442 compared with placebo in patients

with type 2 diabetes mellitus inadequately controlled by diet and

exercise and up to one oral anti-diabetes agent.

Study Number: THR-1442-C-418

Study Phase: 3

Product Name: EGT0001442 tablet

IND Number: 103822

Indication: Type 2 diabetes mellitus

Investigators: Multiple center Sponsor: Theracos, Inc.

Sponsor Contact: [name].

Theracos, inc.

[name] [contact]

Sponsor protocol representative

[name] [name]

[contact]

[contact]

E-mail: [contact]

	Date
Original Protocol:	02 February 2011

Confidentiality Statement

The following confidential information is the property of Theracos, Inc. As long as the information contained in this protocol has not been published, it may only be used when permission has been obtained from Theracos

SYNOPSIS

Sponsor:

Theracos, Inc.

Name of Finished Product:

EGT0001442 tablet

Name of Active Ingredient:

EGT0001442

Study Title:

Efficacy and safety of EGT0001442 compared with placebo in patients with type 2 diabetes mellitus inadequately controlled by diet and exercise and up to one oral anti-diabetes agent.

Study Number:

THR-1442-C-418

Study Phase: 3

Primary Objective(s):

To assess the efficacy of EGT0001442 in lowering HbA1c at week 24 compared with placebo

Secondary Objective(s):

- To assess the efficacy of EGT0001442 in lowering FPG at weeks 2 and 24 compared with placebo
- To assess the efficacy of EGT0001442 based on the proportion of subjects in the EGT0001442 group reaches the American Diabetes Association (ADA) target HbA1c of <7% compared with placebo
- To assess the effect of EGT0001442 on systolic and diastolic blood pressure compared with placebo
- To assess the effect of EGT0001442 on body weight compared with placebo
- To assess the change in HbA1c change over time, week 1 to week 96
- To assess the safety of EGT0001442 in patients with T2DM

Study Design:

A multinational, 2 arm parallel groups, randomized, double-blind placebo-controlled study to compare the treatment of once daily EGT0001442 at 30 mg with matching placebo in treatment-naïve type 2 diabetic patients (i.e. not taking an antihyperglycaemic agent for ≥16 weeks prior to study entry) or with diet and exercise in combination with one oral antidiabetes drug and an HbA1c of 7-10%. Approximately 300 eligible subjects will start a 2-week placebo run-in period prior to being randomly assigned to either once daily EGT0001442 or placebo in a 1:1 ratio for 24 weeks. Subjects with hyperglycemia may receive approved anti-diabetic medication. At week 24, subjects who have completed the main treatment period will continue to receive study drug until week 96. In the treatment

Confidential

•

extension period, subjects who have elevated HbA1c will have additional antidiabetic therapy added to the study drug consistent with treatment recommendations for type 2 diabetes.

Study Population and main eligibility criteria:

Approximately 300 patients that are inadequately controlled by diet and exercise or by treatment with a single oral anti-diabetes agent, randomized 1:1 to placebo and EGT0001442

- Type 2 diabetes per the American Diabetes Association criteria
- Male or female
- Age \geq 18 years
- Receiving one or no oral anti-diabetic agent and diet and exercise instruction
- HbA1c between 7 and 10% at screening
- Body mass index (BMI) $\leq 37 \text{ kg/m}^2$
- Fasting plasma glucose <250 mg/dL at screening for subjects not treated with oral anti-diabetic therapies
- Fasting plasma glucose <240 mg/dL at screening for subjects treated with antidiabetic therapies
- Fasting plasma glucose <250 mg/dL for all subjects at randomization

Test Product, Dose, and Mode of Administration:

EGT0001442 tablets 30 mg once daily by mouth

Reference Therapy; Dose; and Mode of Administration:

• Placebo – once daily by mouth

Duration of Treatment:

• 98 week (2wk run-in, 24 week primary evaluation, 72 week extension)

Statistical Methods:

The primary objective of this trial is to assess the efficacy of EGT0001442 in treatment-naïve type-2 diabetic patients or patients on a single oral anti-diabetic drug in combination with diet and exercise with an HbA1c between 7 and 10%. Efficacy is defined as a significant reduction in HbA1c at week 24 when compared to placebo. The effect of EGT0001442 on fasting glucose, blood pressure, body weight and the general safety of EGT0001442 in patients with T2DM will also be explored.

Statistical analyses and summaries of safety and tolerability will be performed using SAS® software (SAS Institute, Cary, NC). In all cases, significance will be judged at the α =0.05 level. No multiplicity adjustment will be required for the single primary endpoint.

Date of Original Approved Protocol: 02 February 2011

TABLE OF CONTENTS

SY	YNOPSIS) 	2
LI	ST OF A	BBREVIATIONS AND DEFINITIONS OF TERMS	
N	O OBSEF	RVABLE ADVERSE EFFECT LEVEL	9
1	INTRO	DDUCTION	11
	1.1	EGT0001442 for the treatment of type 2 diabetes mellitus	11
	1.1.	Summary of non-clinical data with EGT0001442	12
	1.1.	2 Summary of Clinical data with EGT0001442	12
2	STUD	Y OBJECTIVES	14
	2.1	Primary Objective(s)	14
	2.2	Secondary Objective(s)	14
3	INVES	STIGATIONAL PLAN	15
	3.1	Overall Study Design and Plan	15
	3.2	Rationale for Study Design and Control Group	17
	3.3	Study Duration and Dates	18
4	STUD	Y POPULATION SELECTION	19
	4.1	Study Population	19
	4.2	Inclusion Criteria	19
	4.3	Exclusion criteria	19
5	STUDY TREATMENT(S)		21
	5.1	Description of Treatment(s)	21
	5.1.	1 Study Drug	21
	5.1.	2 Placebo	21
	5.1.	Rescue medications	21
		Treatments Administered	
		Selection and Timing of Dose for Each Patient	
	5.4	Method of Assigning Patients to Treatment Groups	22
	5.5	Blinding	22
	5.6	Concomitant Therapy	23
	5.7	Restrictions	24
	5.7.	Prior Therapy	24
	5.7.	Fluid and Food Intake	24
	5.7.	Patient Activity Restrictions	24
		Treatment Compliance	
	5.9	Packaging and Labeling	25
	5.9.	1 Study drug for main treatment period	25

	5.9	9.2	Study drug for the treatment extension period	25
	5.10	Stora	age and Accountability	25
	5.11	Inves	estigational Product Retention at Study Site	25
6	STU	DY PF	ROCEDURES	26
	6.1	Infor	rmed Consent	26
	6.2	Medi	lical History	26
	6.3	Phys	sical Examination	27
	6.4	Vital	l Signs	27
	6.5	Elect	trocardiography	27
	6.6	Diet	and exercise counseling	27
	6.7	Clini	ical Laboratory Tests	27
	6.7	7.1	Laboratory Parameters	27
	6.7	7.2	Sample Collection, Storage, and Shipping	
		6.7.2		
		6.7.2		

RBC red blood cell (count)

SAD single ascending dose

Confidential Page 9 of 61

EGT0001442 tablet Theracos, Inc.
Clinical Trial Protocol: THR-1442-C-418 02 February 2011

SAE serious adverse event

SD standard deviation

SMBG self monitored blood glucose

T2DM type 2 diabetes mellitus

TEAEs Treatment emergent adverse events

t_{max} time to maximum concentration

UGE₀₋₂₄ urinary glucose excretion from 0 to 24 h post dose

ULRR Upper Limit of the Reference Range

USP/NF The United States Pharmacopeia–National Formulary

UTI urinary tract infections

WBC white blood cell (count)

WHODRUG World Health Organization Drug Dictionary

WOCBP Women of childbearing potential

1 INTRODUCTION

Diabetes mellitus, characterized by hyperglycemia, is caused by defective insulin secretion, resistance to insulin action, or a combination of both. Approximately 285 million people worldwide, or 6.6%, in the age group 20-79 have diabetes in 2010. The prevalence of diabetes is projected to be 438 million or 7.8% of the adult population by 2030 (Sicree et al., 2010). Over 90% of diabetic patients have type 2 diabetes mellitus (T2DM) and over 80% of the type 2 diabetic patients are overweight or obese. Several classes of agents for type 2 diabetes are available for treating hyperglycemic conditions including insulin secretagogues, PPARγ agonists, metformin, alpha glucosidase inhibitors, glucagon-like peptide 1 (GLP-1) analogues, and dipeptidyl peptidase 4 (DPP4) inhibitors. Insulin and its analogues also are prescribed for the treatment of type 2 diabetes as the disease progresses. However, a rapid rise in the number of adult type 2 diabetics has led to an increasing recognition that additional therapeutic modalities are needed to provide safe and effective reductions of elevated plasma glucose levels.

The renal Na+/glucose transporter SGLT2 (gene name SLC5A2) is a member of a sugar transporter family that actively transports extracellular hexoses into cells using the driving energy of the transmembrane electrochemical potential for sodium ions. Individuals with disruptions in the gene encoding SGLT2 exhibit prominent glucosuria in the absence of significant comorbidities (Santer et al., 2003; van den Heuvel et al., 2002). Significantly, neither hypoglycemia nor an increased incidence of urinary tract infections have been reported in these individuals. The elimination of glucose from the blood via urinary excretion has the potential to improve both fasting and postprandial hyperglycemia without increasing insulin secretion, causing weight gain, or inducing hypoglycemia.

Phlorizin, a natural product inhibitor of SGLT1 and 2, has been shown to produce urinary glucose excretion (UGE) and lower plasma glucose levels in several animal models (Ehrenkranz et al., 2005). Development of phlorizin was discontinued due to its rapid degradation by lactase-phlorizin hydrolase and poor absorption from the gastrointestinal tract. Several SGLT2 inhibitors are in development (Han et al., 2008; Neumiller et al., 2010). Dapagliflozin is the SGLT2 inhibitor with the most extensive clinical data. Early phase studies demonstrated sustained, dose-dependent glucosuria over 24 hours with once daily oral dosing (Komoroski et al., 2009a; Komoroski et al., 2009b). A double blind, placebo controlled study showed that treatment with dapagliflozin for 6 months resulted in 0.58% – 0.89% reduction of glycosylated hemoglobin A1c (HbA1c) from baseline compared with -0.23% in the placebo group with a placebo-subtracted changes in weight up to 1.1 kg (Ferrannini et al., 2010). Increased numbers of urinary tract and genital infections were observed in the treated groups.

1.1 EGT0001442 for the treatment of type 2 diabetes mellitus

EGT0001442, a candidate oral antidiabetic agent, is a potent, highly specific inhibitor of the renal Na+/glucose transporter SGLT2. It is a benzylbenzene C-glycoside of the same

chemical structural class as dapagliflozin. EGT00001442 elicits a prominent and predictable glucosuria in laboratory animals and in healthy and diabetic subjects in clinical studies.

Several previous non-clinical and clinical studies were conducted with EGT0001474, a now-discontinued crystalline formulation of EGT0001442 and L-proline in 1:2 stoichiometry. The mass ratio of EGT0001474 to EGT0001442 is 1.5:1. In this protocol, all studies performed with EGT0001474 are described in terms of the EGT0001442 content. For example if a study used 50 mg of EGT0001474 it is described as 33 mg of EGT0001442 (delivered as proline cocrystal). EGT0001474 and EGT0001442 have similar solubility in water, similar dissolution rates when formulated as capsules, and show similar exposure in rat, monkey, and human studies.

1.1.1 Summary of non-clinical data with EGT0001442

The potential adverse effects of EGT0001442 have been evaluated through safety pharmacology, genotoxicity, acute, chronic, and reproductive toxicity studies. Repeat dose toxicity studies performed in rats, dogs and monkeys found diarrhea and gastric irritation including sporadic ulceration, at the lowest observable effect level. The NOAELs based on these studies are 6.7 and 20 mg/kg/day in rats and monkeys, respectively, representing safety multiples of 8.1 and 19.6 relative to anticipated exposures in diabetic patients at the planned clinical dose of 20 mg/day. Chronic exposures produced similar toxicity profiles, with the additional finding of microvacuolization of renal cortical cells in monkeys after 39 weeks dosing. This microscopic pathology occurred without clinical chemistry correlates, and the renal effects generally reversed during the recovery phase. EGT0001442 does not affect fertility or in utero development up to the maximum tolerated doses in rats and rabbits. Details of the toxicology findings are described in the Investigator's Brochure.

1.1.2 Summary of Clinical data with EGT0001442

Clinical studies have been conducted to evaluate safety, tolerability, pharmacokinetics (PK), pharmacodynamics (PD), metabolism, and efficacy of EGT0001442. No deaths or study drug related serious adverse events (AEs) have been reported in the clinical trials. EGT0001442 up to 100 mg for up to 14 days was safe and tolerated in healthy volunteers. In a phase 2, double-blind, placebo-controlled study, subjects with type 2 diabetes mellitus were treated with EGT0001442 in doses of 5 to 50 mg or a placebo for 28 days. The most frequently occurring AEs were headache (4% in the placebo and 11% in the treatment groups), pollakiuria (none in the placebo and 4% in the treatment groups), fatigue (7% in the placebo and 2% in the treated group), and nausea (4% in the placebo and 3% in the treated group). No hypoglycemia was reported. Genital and urinary tract infections were observed in some subjects in the EGT0001442 treated groups, including balanitis candida, urinary tract infection, bacterial vaginitis, vulvovaginal candidiasis, and vulvovaginal mycotic infection.

Urinary glucose excretion (UGE) was measured in healthy and diabetic subjects. EGT0001442 increased UGE in a dose-dependent and saturable manner. The plateau in UGE corresponded to dosages of EGT0001442 above 20 mg/day. EGT0001442 treatment in subjects with T2DM for 4 weeks was effective in reducing FPG by 24 to 41.6 mg/dL in the

groups dosed with 5 to 50 mg/day EGT0001442. Subjects receiving EGT0001442 also had a reduction in body weight, blood pressure, and postprandial glucose compared to the changes in the placebo group. Details of the safety and efficacy information are described in the Investigator's Brochure

2 STUDY OBJECTIVES

2.1 Primary Objective(s)

The primary objective of this study is to assess the efficacy of EGT0001442 in lowering HbA1c at week 24 compared with placebo.

2.2 Secondary Objective(s)

The secondary objective(s) of this study is (are):

- To assess the efficacy of EGT0001442 in lowering FPG at weeks 2 and 24 compared with placebo
- To assess the efficacy of EGT0001442 based on the proportion of subjects in the EGT0001442 group reaches the American Diabetes Association (ADA) target HbA1c of <7% compared with placebo
- To assess the effect of EGT0001442 on systolic and diastolic blood pressure compared with placebo
- To assess the effect of EGT0001442 on body weight compared with placebo
- To assess the change in HbA1c change over time, week 1 to week 96
- To assess the safety of EGT0001442 in patients with T2DM

3 INVESTIGATIONAL PLAN

3.1 Overall Study Design and Plan

STUDY DESIGN

THR-1442-C-418 is a multinational, 2 arm parallel groups, randomized, double-blind placebo-controlled study to compare the treatment of once daily EGT0001442 at 30 mg with matching placebo in treatment-naïve type 2 diabetic patients (i.e. not taking an antihyperglycaemic agent for ≥16 weeks prior to study entry) or with diet and exercise in combination with one oral antidiabetes drug and an HbA1c of 7-10%. Approximately 300 eligible subjects will start a 2-week placebo run-in period prior to being randomly assigned to either once daily EGT0001442 or placebo, using a computer-generated allocation schedule, in a 1:1 ratio for 24 weeks. Subjects with hyperglycemia may receive approved anti-diabetic medication. At the end of week 24, subjects who have completed the main treatment period will continue to receive study drug until week 96. In the treatment extension period, subjects who have elevated HbA1c will have additional antidiabetic therapy added to the study drug consistent with treatment recommendations for type 2 diabetes. The primary analysis is to assess whether EGT0001442 is superior to placebo based on HbA1c change from baseline to week 24.

RESEARCH METHODS AND PROCEDURES

At screening visit, subjects who meet all the inclusion criteria, none of the exclusion criteria, and who consent to participate in the study will receive counseling for appropriate diet and exercise. Those who are on an oral antidiabetic medication (OAM) will discontinue the medication and receive placebo in this run-in prior for 14 ± 3 days. Eligible diabetic subjects who are treatment naïve and who control their hyperglycemia through diet and exercise will also receive placebo and the hyperglycemia will be monitored to ensure that their fasting blood glucose levels remain below 250 mg/dL during this interval of 14 ± 3 days.

After the run-in period, approximately 300 subjects will complete the baseline assessment on day 1 after overnight fasting to confirm their eligibility. The subjects that remain eligible will be randomly assigned to one of the 2 treatment groups on day 1. Randomization will be stratified by study center and based on screening HbA1c (\geq 7 to <8.5% or \geq 8.5 to 10%). The planned doses are 30 mg/day of EGT0001442 or placebo. Each subject will be provided with study drug for 6 weeks, dosing instructions and log, diet and exercise counseling, and a diary card for recording food and fasting glucose information on the days prior to each clinic visit.

Each subject will be instructed to return to the clinic on weeks 2, 6, 12, 18, and 24 for safety monitoring and efficacy assessment including review of adverse events, concomitant medication, ECG, vital signs, physical examinations, testing of blood chemistry and hematology laboratory parameters, and a urinalysis.

Subjects who complete the 24-week treatment period will continue receiving the study drug for an additional 72 weeks. Subjects who receive rescue medication due to poor glycemic

control will continue to receive approved anti-diabetic medications and standard of care per investigator decision according to current treatment guidelines for 72 weeks. In the treatment extension period, subjects must return to the clinic on weeks 36, 48, 60, 72, 84, and 96 for continuous safety monitoring and efficacy assessment, including review of HbA1c values, adverse events, concomitant medication, ECG, vital signs, and physical examinations. A follow up exit visit will be conducted at 1 week after the last dose. Subjects will be advised to see their primary physician and resume standard of treatment to control diabetes.

GLYCEMIC CONTROL

During the run-in period, subjects will be instructed to determine daily self-monitored blood glucose (SMBG) after an overnight fast. The SMBG record will be reviewed by the investigator at each clinic visit. If the fasting blood glucose is > 216 mg/dL (12 mmol/L) in two consecutive days, the subject should contact the clinical staff. In addition, subjects will be instructed that they must contact the clinic within 24 h if SMBG is ≥ 270 mg/dL (15 mmol/L). If the fasting SMBG is ≥ 270 mg/dL (15 mmol/L) without explanations for the elevation, the investigator will review the SMBG record and determine if the subject should attempt to improve diet and exercise to maintain glycemic control or if the subject must discontinue from the study and resume diabetic medications. Subjects with symptomatic hyperglycemia or hypoglycemia should be withdrawn if the symptoms are severe.

During the 24-week main treatment period, study subjects will be advised to continue daily SMBG measurements and contact the clinic if the SMBG is \geq 270 mg/dL (15 mmole/L) from week 1 (week of randomization) to week 6, \geq 240 mg/dL (13.3 mmole/L) from week 6 to week 12, or \geq 200 mg/dL (11.1 mmole/L) from week 12 to week 24. During the 72-week extension period (weeks 25 to 96), subjects will continue to monitor the SMBG and contact the clinic if SMBG is \geq 200 mg/dL (11.1 mmole/L). Values of HbA1c will be evaluated in the extension period by the investigator and approved standard of oral therapy will be prescribed if HbA1c is elevated.

The investigator must review the SMBG record and FPG values in every clinic visit and assess whether any subject should receive rescue medications to treat the hyperglycemic condition during the 24-week main treatment period. The subject must be queried to assess compliance with a minimum of a 10 h fast prior to blood draw to ensure the FPG values can be accurately determined. If a subject has not fasted for 10 h, the subject must return within a week after proper fasting. The investigator will provide diet and exercise counseling and determine if the subject should receive additional rescue medication as a result of the glucose. A serum sample must be drawn prior to the rescue medication so that the last HbA1c value while the subject is on study drug only can be carried forward to 24 weeks for the primary end point analysis.

OTHER SAFETY MONITORING ACTIVITIES

The safety monitoring activities will include vital signs, physical examinations, urinalysis, adverse events, and concomitant medication use. The occurrence of blood, liver, or skin disorders will be monitored through laboratory testing and adverse event documentation.

Adverse event of special interests will include any clinical signs and symptoms indicating either upper or non-upper urinary tract infections (UTIs) and genital infections. Any adverse events that mapped to UTIs or genital infections must be documented.

DATA AND SAFETY MONITORING BOARD (DSMB)

An independent Data and Safety Monitoring Board (DSMB) will monitor the overall safety information during the EGT0001442 development. The safety review activity and potential risk benefit assessment will be defined in the charter.

MAJOR ADVERSE CARDIOVASCULAR EVENT ADJUDICATION

An independent cardiovascular adjudication committee is established to review the cardiovascular events during the study in a blinded fashion. These events include cardiovascular mortality, myocardial infarction, stroke, and hospitalization for acute coronary syndromes, urgent revascularization procedures, and, other possible serious cardiovascular events. The adjudicated events will be documented and archived to allow a meta-analysis to be performed to assess if there is any increase of cardiovascular risk to an unacceptable extent at the time of completion of all phase 3 clinical studies.

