5.5 Blinding

The study drug will be blinded to the sponsor, investigators, study coordinators, pharmacists, study subjects, and the cardiovascular adjudication committee members. Upon randomization, each subject will receive a subject randomization number and a drug kit

assigned to the subject. To maintain blinding of the treatment, the values of the HbA1c after dosing starts will remain blinded to all study personnel and patients until all subjects have completed the 24 week treatment period.

If knowledge of the test substance is needed to manage the subject's condition, the investigator will contact the IVRS to obtain the treatment assignment. If unblinding occurs, the time and reason for unblinding will be recorded on the CRF and the sponsor must be notified within 24 h.

A designated statistician who is not involved with the study operation will hold the treatment code. The unblinded treatment information can be provided to the DSMB to facilitate the evaluation of any clinically important increase in the rate of a serious suspected adverse reaction or to the designated safety contact when the treatment information is required to determine if an expedited safety report must be submitted to regulatory agencies. The treatment code will be unblinded when the clinical database is locked and data are to be analyzed.

The treatment assignment will continue to be withheld from the cardiovascular adjudication committee members at the conclusion of the study until all phase 2 and phase 3 investigational studies are completed and a meta-analysis to assess cardiovascular risk is conducted.

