Subjects who complete the 24-week treatment period will continue receiving the study drug for an additional 72 weeks. Subjects who receive rescue medication due to poor glycemic control will continue to receive approved anti-diabetic medications and standard of care per investigator

Final – 22November2011 CONFIDENTIAL Page 8 of 30

decision, according to current treatment guidelines, during the 72 week follow-on period. In the weeks 25 to 96 treatment period, subjects must return to the clinic on weeks 36, 48, 60, 72, 84, and 96 for continuous safety monitoring and efficacy assessment, including review of HbA1c values, adverse events, concomitant medication, ECG, vital signs, and physical examinations. A follow up exit visit will be conducted one week after the last dose.

The overall study duration from screening until follow-up could last a maximum of 102 weeks for study subjects.

An independent Data and Safety Monitoring Board (DSMB) will monitor overall safety information during the EGT0001442 development program including this study. The safety review activity and potential risk benefit assessments utilized by the DSMB are documented in DSMB charter and a separate DSMB statistical analysis plan.

An independent cardiovascular adjudication committee is established to review cardiovascular events (CVE) occurring during the study, in a blinded fashion. These events include cardiovascular mortality, myocardial infarction, stroke, and hospitalization for acute coronary syndromes, urgent revascularization procedures, and other possible serious cardiovascular events. The adjudicated events will be documented and archived to allow a meta-analysis to be performed to assess if there is any increase in cardiovascular risk to an unacceptable extent at the time of completion of all phase 2 and 3 clinical studies. The evaluation and analysis of adjudicated cardiovascular events will be documented in a separate CVE statistical analysis plan.

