### 3.4 Blinding, Randomization, and Bias

Eligible subjects who complete the  $14 \pm 3$  day run-in period and meet all study inclusion/exclusion requirements will be randomized in a 1:1 ratio to receive EGT0001442 20 mg/day or placebo according to a computer-generated randomization schedule. Subjects will be assigned to treatment groups in sequential order as they qualify for the study, using a centrally located and managed interactive web response system (IWRS). Randomization will be stratified by study center and screening HbA1c ( $\geq 7$  to < 8.5% or  $\geq 8.5$  to 10%). The study will be conducted at multiple investigative sites and will likely involve variable numbers of subjects at each site. Enrollment will be on a competitive basis but each site will be capped at 15% of the total randomized subjects (45 subjects).

The study drug will be blinded to the sponsor, investigators, study coordinators, pharmacists, study subjects, and the cardiovascular adjudication committee members. Upon randomization, each subject will receive a subject randomization number and drug kit(s) assigned to the subject. To maintain blinding of the treatment, the values of the HbA1c after dosing starts will remain blinded to all study personnel and subjects until all subjects have completed the 24 week treatment period. After all subjects have completed the 24 week treatment period, all previous and subsequent HbA1c values will be made available to the sponsor, investigators, study coordinators, pharmacists, and the study subjects for close monitoring of subjects' safety including assessment of providing rescue medication. Subjects' treatment assignment will continue to be held from all study personnel so the remainder of the study can be conducted in a blinded fashion.

If knowledge of the test substance is needed to manage the subject's condition, the investigator will contact the IWRS to obtain the treatment assignment. If unblinding occurs for any reason, the time and reason for unblinding will be recorded on the case report form (CRF) and the sponsor must be notified within 24 hours.

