## 7.2 Secondary Efficacy Analyses

## 7.2.1 HbA1c Change from Baseline over Time

The continuous secondary efficacy endpoint of HbA1c change from baseline by visit will be analyzed analogous to the primary endpoint using a 2 sample t-test. One analysis will be performed using the LOCF algorithm for all visits, and a separate analysis will be performed using OC algorithm. The OC algorithm analysis will exclude any post-rescue values.

Final – 22November2011 CONFIDENTIAL Page 21 of 30

The pattern of HbA1c over time and change from baseline over time will be evaluated both descriptively using summary statistics and graphically at each scheduled visit during the entire duration of the study, excluding post-rescue measurements. Descriptive summaries will also be provided including post-rescue measurements.

The analyses will be performed on the full analysis set and all data will be listed.

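### HbA1c stays masked until the last subject finishes Week 24, so the plan's HbA1c treatment rule cannot be followed for earlier enrollees already in the extension

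*Protocol*

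**What the plan says.** **Masking rule.** Protocol 5.5 states that post-dose HbA1c values "will remain blinded to all study personnel and patients until all subjects have completed the 24 week treatment period". SAP 3.4 keeps this and describes the release: "After all subjects have completed the 24 week treatment period, all previous and subsequent HbA1c values will be made available" to the sponsor, sites and subjects. It gives the purpose as close safety monitoring, including decisions on rescue medication.

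**Treatment rule.** Protocol 3.1 continues each subject on study drug once that subject has completed 24 weeks. It then says: "In the treatment extension period, subjects who have elevated HbA1c will have additional antidiabetic therapy added to the study drug". Visits at Weeks 36, 48, 60, 72, 84 and 96 are "for continuous safety monitoring and efficacy assessment, including review of HbA1c values". Under Glycemic Control, the same section says "Values of HbA1c will be evaluated in the extension period by the investigator", with oral therapy to be prescribed if HbA1c is elevated. No number defines elevated.

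**SAP on the extension visits.** SAP 3.1 repeats the visit schedule up to Week "96 for continuous safety monitoring and efficacy assessment, including review of HbA1c values". It does not repeat the instruction to prescribe.

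**The concern.** The release date is set by the whole trial, while the duty to review and treat is set by each subject's own clock. An investigator cannot evaluate a value that is withheld, so both rules can be followed only if everyone enrolls at nearly the same time.

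Protocol 3.2 names three monitoring tools meant to prevent prolonged hyperglycemia: self-monitored blood glucose (SMBG), fasting plasma glucose (FPG) and HbA1c. For part of the extension the third is missing. Prior oral therapy was stopped at run-in (Protocol 7.1.2) and half the subjects are on placebo. A subject whose HbA1c is elevated but whose SMBG stays below 200 mg/dL meets no other stated trigger in the extension.

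There is also a smaller effect on analysis. Rescue counts by time band (SAP Table 14.1-3.4) and HbA1c summaries without post-rescue values (SAP 7.2.1: "The OC algorithm analysis will exclude any post-rescue values") would combine two rescue regimes. Before the release date rescue is triggered by glucose alone; after it, by glucose or HbA1c.

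**Working it through.** **Is there an interim route?** Neither document gives a per-subject release, a laboratory HbA1c alert or an unmasked HbA1c reviewer. The emergency code break (Protocol 5.5 and 6.9.5) reveals treatment assignment, not HbA1c. The duty to review SMBG and FPG for rescue in Protocol 3.1 is worded for the 24-week main period. FPG is still drawn and SMBG still reviewed at extension visits (Protocol 7.3), but the only numeric trigger stated for the extension is clinic contact at SMBG of 200 mg/dL or more.

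**How long is the gap?** The plan gives no figure to reproduce. Protocol 3.3 says only that overall duration depends on accrual, so accrual length is an assumption here.

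Inputs:
- Release occurs when the last subject completes Week 24 (Protocol 5.5, SAP 3.4).
- The extension runs 72 weeks, with visits at Weeks 36, 48, 60, 72, 84 and 96 (Protocol 3.1).
- Assumed: uniform accrual over A weeks, with A = 12, 26 or 52. Visit windows and laboratory turnaround are ignored.

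For a subject enrolled at time x, release comes at calendar week A + 24.
- Masked extension time = min(A − x, 72). For A up to 72 its mean is A/2.
- The visit at Week w is masked if x + w < A + 24, so the share of subjects masked is max(0, [A − (w − 24)]/A).

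| | A = 12 | A = 26 | A = 52 |
|---|---|---|---|
| Mean masked time (weeks of 72) | 6 | 13 | 26 |
| Masked at Week 36 | 0% | 14/26 = 53.8% | 40/52 = 76.9% |
| Masked at Week 48 | 0% | 2/26 = 7.7% | 28/52 = 53.8% |
| Masked at Week 60 | 0% | 0% | 16/52 = 30.8% |
| Masked at Week 72 | 0% | 0% | 4/52 = 7.7% |
| Masked at Weeks 84 and 96 | 0% | 0% | 0% |
| Mean masked visits, of six | 0 | 16/26 = 0.62 | 88/52 = 1.69 |

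For the first enrollee the gap is the full A weeks: release comes at that subject's own Week 36, 50 or 76. With A of 12 or less, no scheduled extension visit falls before release, but the Week 24 value is still unavailable when earlier enrollees enter the extension.

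**Any hint of the real accrual length?** The SAP shell for Table 14.1-1.3 tabulates run-in failures under protocol versions dated 11 April 2011 and 18 August/12 September 2011. These dates are 129 and 154 days apart, or 18.4 and 22.0 weeks. This suggests screening lasted more than 12 weeks but does not prove it.

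**The case against.** The best reply is that the sponsor chose this deliberately. SAP 3.4 links HbA1c-guided rescue to the trial-level release, which protects the blind while other subjects are still in the primary period. On that view, Protocol 3.1 means HbA1c is used in the extension once it is available. But Protocol 3.1 does not say so. It defines the extension by subject week, 25 to 96, and lists HbA1c review from Week 36.

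Several other points stand:
- The SAP repeats only the review, not the instruction to prescribe. That instruction is confirmed only in the February 2011 protocol, and the later versions are not available.
- The size of the gap rests on assumed accrual and could be small.
- SMBG contact at 200 mg/dL, FPG and the DSMB give real safety cover. The same SMBG threshold operates with HbA1c masked in Weeks 12 to 24.
- Extension analyses are secondary or exploratory, with nominal p-values. Extension rescue already depends on investigator judgment.
- An alert on one subject reaches a site where others may still be before Week 24. Rescue in that period decides which HbA1c value is carried into the primary analysis (Protocol 9.5.1, SAP 7.1). This risk is real but small, because investigators already see FPG and SMBG, which carry similar information.

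These points limit the seriousness of the conflict without resolving it.

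**Conclusion.** The concern holds. As written, the HbA1c treatment rule cannot be applied to any subject between their own Week 24 and the last subject's Week 24. The SAP keeps both the visit-level review and the trial-level release, so it does not remove the problem.

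Under uniform accrual of 12 to 52 weeks, the mean delay is 6 to 26 weeks and 0 to 1.7 of the six extension visits are masked. These figures depend entirely on the assumed accrual. The consequence is delayed treatment for subjects whom HbA1c alone would identify, plus some mixing of rescue regimes in the extension summaries. The primary result is not threatened. The point is worth correcting because the plan's own safety rule cannot operate and the remedy is cheap.

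**What to change.** Amend Protocol 5.5 and SAP 3.4 so that full masking of HbA1c ends for each subject once that subject's Week 24 sample has been drawn. From then until the existing trial-level release, the central laboratory would send the investigator only an alert when a Week 24 or later HbA1c exceeds one sponsor-set threshold, identical in both arms. Put the same threshold in Protocol 3.1 so that elevated has a number. After the trial-level release, full values become available as SAP 3.4 already provides. Treatment assignment stays masked throughout.

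The cost is wording in two documents and an alert setting at the laboratory. The drawback is that sites learn that some subjects are above the threshold before the Week 24 data are cleaned and locked (SAP 3.6.1). Withholding the values themselves limits this, and the alerted subject's primary-endpoint sample has already been taken.
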